Because of the antihypertensive effect of doxazosin, it is important that participant blood pressure be adequately monitored. Participants will also be assessed for orthostatic hypotension based on supine and standing blood pressure. Orthostatic hypotension is defined as a decrease in the systolic blood pressure of greater than 20 mmHg or a decrease in the diastolic blood pressure of greater than 10 mmHg between the supine and standing positions, or the development of significant postural symptoms.

2. Prostate Specific Antigen

Serum prostate specific antigen (PSA) assays will be performed by the Diagnostic Center at baseline, 12 months and yearly thereafter. The baseline serum PSA collected at screening visit #1 (SV1) will be reported directly back to the corresponding clinical center to determine participant eligibility and need for biopsies prior to randomization.

Follow-up PSA values will be reported by the Diagnostic Center directly to the Biostatistical Coordinating Center (BCC) where the BCC will apply a correcting algorithm prior to reporting the PSA value to the corresponding clinical center. The correction algorithm will be: (1) for participants on placebo or doxazosin only, the PSA value will be multiplied by one and (2) for participants on finasteride only or finasteride plus doxazosin, the PSA value will be multiplied by two plus a correction factor for odd-numbered values. Both the Diagnostic Center and individual clinical centers will remain masked to treatment assignment.

Decisions based on the PSA value concerning the need for additional prostate biopsies, other than those scheduled in the prostate biopsy substudy, will be left to the discretion of the clinical center's principal investigator.

3. Treatment Emergent Adverse Events

Reporting of adverse events will be accomplished by collecting information on adverse experiences at each follow-up visit. Occurrence of an adverse event will be indicated on the standard follow-up visit case report form and detailed on the adverse event report form.

In order to facilitate timely reporting of certain serious adverse events, the Adverse Event Report will be filled out immediately and directed to the BCC, where the BCC medical consultant will serve as the serious adverse event report monitor. It is important to note that all serious adverse events should be reported in this way,

regardless of whether the adverse event is suspected to be related to study medication. 1 A "serious" adverse event is defined as one which is: 2 3 1. fatal or life threatening 2. permanently disabling 4 5 3. requiring or prolonging inpatient hospitalization 6 4. a congenital anomaly or cancer 7 5. an overdose 8 In accordance with the FDA Guidelines effective April 6, 1998, the following additional category is added to the definition: 9 10 6. important medical events that may not result in death, be life-threatening or require hospitalization if, based on appropriate medical judgement, they 11 may jeopardize the patient and may require medical or surgical 12 intervention to prevent a serious adverse event. 13

1			SECTION 7		
2			Data Processing		
3	A.	Case	e Report Forms (CRFs)		
4		Case	e report forms will be filled out at each visit to collect participant data.		
5	1.	Base	Baseline Forms		
6		1.	Eligibility/Exclusion Inventory		
7 8 9		2.	Screening Visit 1: Medical History, Vital Signs, Physical Examination, Urinary Flow Rates, Local Laboratory Results (Urinalysis and Hematology/Chemistries).		
10		3.	Screening Visit 2: Vital Signs and Urinary Flow Rates.		
11		4.	Randomization Visit: Vital Signs.		
12		5.	Recruitment Source Tracking		
13	2.	Follo	ow-up Forms		
14 15 16		1.	Standard Follow-up Visit Inventory: Vital Signs, Urinary Flow Rates, Compliance, Adverse Events, and Concomitant Medications (administered at every participant visit except for titration visits)		
17 18		2.	Major Follow-up Visit Inventory: Physical Examination and Local Laboratory Results (administered yearly)		
19		3.	Interim Visit Checklist: Vital Signs, Compliance, and Intercurrent Illness.		
20		4.	Missed Follow-Up Visit Report		
21 22		5.	Titration Visit Inventory: Vital Signs, Compliance, Adverse Events (administered at end-weeks 3 and 4 of any titration period)		
23	3.	Othe	er Specific Forms		
24		1.	AUA Symptom Questionnaires		

1		2.	Sexual Function Questionnaire		
2		3.	MOS-36 Health Survey Questionnaire		
3		4.	Prostatitis Questionnaire		
4		5.	PSA Collection Report		
5		6.	TRUS/Biopsy Data		
6		7.	Non-scheduled Biopsy Information		
7		8.	Missed Biopsy Report		
8		9.	Significant Clinical Events		
9		10.	Adverse Event Report		
10		11.	Patient Tracking Information		
11		12.	Medication Run-In Information		
12		13.	Clinic Laboratory Normal Range Report		
13		14.	Clinic Review Committee Report		
14		15.	Prostate Cancer Registry Report		
15		16.	Prior Use of Viagra Report		
16	4.	End-d	of-Study Forms		
17		1.	Post End-of-Study Visit Inventory		
18		2.	Final Status Report for Inactive Participants		
19 20 21 22 23	The case report forms are created centrally at the BCC and sent to the clinics. The clinic coordinators fill out the forms and enter them into the local microcomputer. The forms will be edited as they are entered into the microcomputer-based remote data management system.				

B. Remote Data Management System

24

1. Clinical Centers

 The microcomputer remote data management system consists of a network of microcomputers, one at each clinical center and one at the BCC. Hardware includes Dell microcomputers and auto-answer, auto-dial modems. Data entry software corresponding to the CRFs completed at a clinical center will be developed and maintained by the staff at the BCC. Data will be entered by clinical center staff and transmitted weekly via telecommunications link to the BCC.

2. Diagnostic Center

A single microcomputer will be located at the Diagnostic Center, which will include a Dell microcomputer and an auto-answer, auto-dial modem. Data entry software corresponding to the analyses performed at the Diagnostic Center will be developed and maintained by the staff at the BCC. Data will be entered by diagnostic center staff and transmitted weekly via telecommunications link to the BCC.

C. Centralized Data Management System

Data will be transmitted weekly from the clinical centers and the Diagnostic Center to the BCC and uploaded to the mainframe and converted to SAS data sets. All new data will be edited weekly for unavailable, out of range, or inconsistent values. Monthly audit programs will produce more detailed edits across all forms for an individual participant. Summaries will be prepared for reports to the Steering Committee.

D. Performance Monitoring

1. Training Workshop and Site Visits

The BCC will establish procedures to train and certify clinical investigators in the MTOPS protocol and data processing procedures. Prior to the initiation of recruitment for the full-scale clinical trial, a workshop will be held at which time the personnel from the clinical centers will be trained in the appropriate study procedures including the use of the case report forms and data processing systems. At that time, Diagnostic Center personnel will instruct the coordinators on proper packaging and mailing of specimens for analysis by the Diagnostic Center. The BCC will maintain close contact with the clinic coordinators and will provide additional training or review as needed.

In addition to a training workshop, each of the clinical centers will be visited by clinical monitors. Appropriate representatives from the BCC, the Diagnostic Center, the NIDDK, and other experts will visit the clinical centers, as required. These site visits will review procedures with the clinic coordinators/technicians, assess proficiency in executing the study protocol, review deficiencies detected in monitoring the

performance of the clinical centers, review the utilization of personnel relative to the amounts budgeted, and receive feedback on the adequacy of the centralized support operations.

2. Periodic Performance Reports

During the full-scale clinical trial, the BCC will monitor the performance of the clinical centers and produce periodic reports summarizing protocol performance.

a. Recruitment

The performance of the clinical centers in recruiting eligible BPH participants will be carefully monitored by the BCC. Monthly recruitment summaries will be issued to the Steering Committee throughout the recruitment and randomization period showing the number of potential participants screened, number randomized, and reasons for ineligibility or refusal to participate by clinical center. The reasons for ineligibility will be compared among the clinical centers, and if large differences are found, explanations for these differences will be sought. If the randomization rate falls below the desired number of participants per month, data on reasons for ineligibility and refusal will be used to try to identify strategies that would increase the randomization rate.

b. Baseline Data

Reports to the MTOPS Steering Committee will consist of comparisons between the treatment groups and clinical centers in the characteristics of the participants. If differences are found among the clinical centers, procedures at each center will be reviewed to attempt to distinguish between differences in the participant population and differences caused by variation in the participant selection or measurement techniques.

c. Case Report Form Completion

The BCC will prepare reports for the MTOPS Steering Committee presenting tabulations for the number of forms received, the number of edit messages, and the number of overdue forms and responses to edits. Missing data, particularly on outcome variables, will effectively reduce the power of analyses. In fact, systematic patterns of missing data could bias the results of the trial. Therefore, many of the procedural details outlined in the operations manual are designed to minimize the amount of missing data. The item-specific missing value rate on each CRF will be monitored throughout the full-scale clinical trial.

d. Other Reports

The BCC will prepare reports for the MTOPS Steering Committee on participant

- compliance with the protocol and inactive follow-up. Other reports will be developed, as needed, based on requests from the Steering Committee and associated 1
- 2
- 3 subcommittees.

1 SECTION 8

Statistical Considerations

A. Sample Size and Power

1. Sample Size Requirement

In the full-scale trial, a total number of 2,448 participants will be needed (612 per treatment group) in order to have 80 percent power to detect a one-third reduction in the time to clinical progression of BPH in an active drug group compared to the placebo group (α = 0.05, two-sided). This figure includes a Bonferroni adjustment (Miller, 1981) to control the probability of a Type I error for three pairwise comparisons, i.e., each treatment group versus the placebo. The sample size formula used is found in Lachin and Foulkes (1986, eq. 6.2), which assumes an exponential cumulative incidence distribution with a 25 percent incidence over five years (i.e., hazard rate in the placebo group of 5.8 percent per year). Also assumed is that the randomization period will last 2 years and there will be 4 to 6 years of follow-up per participant.

Long-term clinical trials clearly demonstrating the probability of disease progression over time are lacking. A study by Craigen et al. (1969) suggests that 50 percent of participants will have progression of disease necessitating active treatment within a five year time frame. This study may overestimate the true probability of progression, since this group of participants had severe symptoms at entry. The Veterans Administration Cooperative Trial of watchful waiting versus surgery, as yet unpublished, demonstrated an overall failure rate of 18 percent in the watchful waiting group over three years. Using these two figures as a range, the rate of progression of 25 percent over 5 years in this protocol was obtained.

Information received from the Olmsted County BPH Trial (personal communication, [name].) indicated that 13.5 percent of the cohort of men between 50 and 80 with an initial AUA symptom score of 8 or more and an initial flow rate of 15 mL or less had an increase of 4 or more in their AUA symptom score within 3.5 years of follow-up; this equates to an exponential cumulative incidence over five years of 19 percent. The Veterans Administration study and, α-blocker and finasteride studies have demonstrated a one percent probability of retention per year in participants managed on placebo and watchful waiting. Likewise, the probability of the development of renal insufficiency, recurrent urinary tract infections and urosepsis Pis estimated to be approximately one percent per year.

a. Adjustment for Losses to Follow-up

In any clinical trial, losses to follow-up are inevitable. One should build the losses to follow-up into the sample size calculation to ensure that power will not be reduced substantially (Lachin and Foulkes, 1986). Assuming an exponential loss to

follow-up hazard rate of 5 percent per year, one would adjust the necessary sample size to 2,752 (688 per treatment group). Because we are interested in detecting a 33 percent difference in a "real world" setting, rather than a 33 percent pharmacologic difference, no adjustment for treatment non-compliance will be made. Therefore, the total sample size goal for the full-scale trial is 2,800 participants (700 per treatment group.

2. Factors Affecting Study Power

The power of the study can be affected if the sample size differs from the goal of 2,800. For example, if all other parameters are kept constant, but the attained total sample size is only 2,400 (600 per treatment group), the power drops to 72 percent. A total sample size of 2,000 (500 per treatment group) will give 63 percent power.

While we give 25 percent as the incidence rate over a five year period in the placebo treated group, the data to support this assumption is minimal. If the actual incidence rate is less, power will be less. For example (assuming a sample size of 2800), if the incidence rate is only 20 percent over five years, power decreases to 69 percent. At the 15 percent incidence rate, power is only 54 percent. However, if the actual incidence over five years in the placebo group is 30 percent, power increases to 87 percent.

B. Interim Analysis Method

The Lan-DeMets (1983) spending function approach will be used to adjust the probability of a Type I error for testing the primary study hypothesis when interim "looks" of the data are taken by the External Advisory Board. The Lan-DeMets procedure is flexible, in that the number of looks does not have to be specified in advance, the time interval between looks does not have to be the same throughout the trial, and, if necessary, it is easy to switch from occasional to continuous monitoring of the data at any point during the trial (Lan, Rosenberger, and Lachin, 1993).

The rate at which the Type I error is spent is a function of the fraction of total information available at the time of the interim analysis (i.e., information time). For an interim analysis using the logrank test (i.e., time to BPH progression), the information time is the fraction of the total number of BPH progression events to be accrued in the entire trial. Since the total number of events to be accrued is unknown, an estimate of the information time will be used based on the fraction of total patient exposure (Lan and Lachin, 1990).

C. Statistical Analysis Plan

The principal analyses of primary and secondary endpoints will employ the "intent-to-treat" approach (Peduzzi, Wittes, et al., 1993). The intent-to-treat analyses will include all randomized patients. All statistical tests will be two-sided. The overall

significance level of the primary endpoint will be α = 0.05. However, because interim analyses will be conducted throughout the trial, the significance levels used in the interim and final analyses of the primary endpoint will be adjusted to account for the multiplicity of interim analyses.

Baseline Characteristics. Analysis of homogeneity of baseline characteristics among the four treatment groups will be carried out using standard nonparametric statistical techniques, such as Fisher's exact test for categorical data (Agresti, 1990), and the Kruskal-Wallis test for ordinal or continuous data (Conover, 1980).

Primary Endpoint. Survival analysis techniques (Miller, 1981) such as the Kaplan-Meier survival estimates, the logrank test, and the Cox proportional hazards model to adjust for baseline or time-dependent covariates will be used to compare the treatment groups with respect to time to clinical progression of BPH. It should be noted that under the urn randomization scheme, the usual logrank variance is overestimated, so the logrank test will be more conservative. This is especially true if time trends are present in the data. For this reason, the correct permutational variance can be used in lieu of the logrank variance (Wei and Lachin, 1988). For the primary endpoint analysis, participants will be considered "administratively censored" if they complete the full duration of the trial without clinical progression of their BPH. Participants who prematurely discontinue their follow-up visits prior to documented clinical progression of their BPH will be "censored" as of their last follow-up visit.

Crossover to known invasive therapy prior to clinical progression of BPH may be considered a competing risk event (Lagakos, Lim and Robins, 1990). To account for crossover to known invasive therapy as a competing risk event, the treatment groups will be compared on the composite event defined as clinical progression of BPH or crossover to known invasive therapy, whichever occurs first, using the same methods described above for the primary endpoint.

Secondary Endpoints. Longitudinal data analysis techniques will be used to analyze repeated measures data (e.g., AUA symptom score, MOS-36 Health Survey score and maximal uroflow). Data will be compared across treatment groups using the nonparametric procedures of Wei and Lachin (1984) for two-group comparisons. The parametric linear random effects model of Laird and Ware (1982) can also be used to compare participant slopes over time under a linearity and normality assumption. For non-normal variates, techniques developed by Liang and Zeger (1986) can be used to compare participant slopes under a generalized linear models framework.

1 **SECTION 9** 2 **Study Administration** 3 A. **Organization and Funding** 4 MTOPS is being conducted by a cooperative effort among the NIDDK, the 5 clinical centers, a diagnostic center, and a biostatistical coordinating center. The mechanism of funding is a cooperative agreement from NIDDK. 6 7 1. **Participating Centers Clinical Centers** 8 a. 9 There are 17 clinical centers participating in the cooperative agreement. The Principal Investigators representing the clinics have agreed to abide by study protocols 10 11 and, in addition, to have comparable staff, facilities, and equipment. 12 b. **Diagnostic Center** 13 The Diagnostic Center (DxC) will be the central repository for tissue and serum 14 samples collected during the trial. The DxC will serve as the central laboratory for 15 MTOPS, and will be responsible for collection and analyses of specimens listed in Appendix E. They will serve as the monitor of quality control to ensure uniform 16 17 performance of the biopsy substudy procedures among the clinical centers. **Biostatistical Coordinating Center** 18 C. 19 The Biostatistical Coordinating Center (BCC) is responsible for all aspects of 20 biostatistical design, analysis, and data processing of the clinical trial. In collaboration 21 with the Steering Committee, the BCC is responsible for document processing of the protocol and manual of operations and data collection forms development and testing. 22 The BCC monitors protocol performance, and conducts the interim and final statistical 23 24 analyses. The BCC collaborates with Steering Committee members in the preparation 25 of publications based on the study results. 26 B. **Committees** 27 1. **Steering Committee** 28 The Steering Committee is the policy and decision making group, and will

oversee the administrative aspects of the trial. The Steering Committee is comprised of

29

- 1 a Principal Investigator from each of the clinical centers, the Principal Investigators of
- the BCC and Diagnostic Center, and the NIDDK Project Officer. A chairperson is
- anamed in a non-voting capacity. Each of the Steering Committee members has a
- 4 named alternate. The Steering Committee has primary responsibility for development
 - and conduct of the study protocol and manual of operations (including implementation
- 6 and monitoring).

2. Executive Committee

Although the Steering Committee is the decision and policy making group of the trial, a smaller group has been appointed to direct the day-to-day activities. This committee includes the Chair of the Steering Committee, the NIDDK Project Officer and the Principal Investigators of the BCC and DxC. The committee will meet by telephone conference, as necessary.

3. External Advisory Board

An External Advisory Board, a group of individuals not affiliated with any of the institutions in the cooperative agreement, is established by the NIDDK. The Board will serve as external reviewers and advisors to the NIDDK and the Steering Committee. This Board is charged with reviewing the protocol with respect to ethical and safety standards. Its principal responsibility will be to monitor the emerging results of the full-scale trial to assess treatment effectiveness, or ineffectiveness, and participant safety. The Chair of the Steering Committee, the NIDDK Project Officer and the staff of the BCC are ex-officio members of the Board.

4. Subcommittees

Subcommittees of the Steering Committee are appointed to assume specific responsibilities to help guarantee the successful implementation, monitoring and administration of the trial. Appointed subcommittees include the following: Clinical Review Subcommittee, Recruitment and Retention Subcommittee, Prostate Biopsy and PSA Subcommittee, Publications and Ancillary Study Subcommittee and Trial Coordinators Subcommittee. These subcommittees will consist of members of the MTOPS study group. Their roles and responsibilities are detailed in the Manual of Operations.

1	SECTION 10					
2	Study Timetable					
3 4	The outline below summarizes the timeline for the NIH-BPH pilot study and MTOPS full-scale trial:					
5	PILOT STUDY:					
6	Development Phase 01OCT1992 to 30NOV1993 (14 months)					
7	Randomization Phase 01DEC1993 to 30NOV1994 (12 months)					

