SECTION 3 1 2 **Objectives** 3 Α. **Primary Research Questions** 4 The primary objective of MTOPS is to ascertain if medical therapy (finasteride 5 and/or doxazosin) delays or prevents the progression of BPH. The primary outcome will be the time to clinical progression of BPH. Participants will be classified into one of 6 7 four categories: 8 I. Clinical progression of BPH, as defined by one of the following: 9 1. Acute urinary retention (defined in Appendix F). 10 2. Renal insufficiency due to BPH, as indicated by a 50% increase from 11 baseline in serum creatinine to at least 1.5 mg/dL confirmed within 4 12 weeks. 13 Recurrent urinary tract infections or urosepsis (defined in Appendix F). 3. 14 4. Incontinence (defined in Appendix F). 15 An increase from baseline in the AUA symptom score index of 4 or more 5. points confirmed 2 to 4 weeks later. 16 17 18 II. Crossover to known invasive therapy, prior to clinical progression (as defined in 19 category I). 20 III. Non-compliance with the coded medication treatment regimen, including participants who elect watchful waiting or open-labeled medical therapy 21 including inhibitor of 5- α -reductase or blocker of α -1 adrenoreceptors. 22 23 IV. Completion of study. 24 Participants classified into category I (clinical progression of BPH) because of acute 25 urinary retention, renal insufficiency due to BPH, recurrent urinary tract infections, urosepsis or incontinence will be taken off coded medication but will continue their 26 27 scheduled follow-up visits, if possible. Participants classified into category I because of 28 an increase in the AUA symptom score will be taken off coded medication at the 29 discretion of the clinical center's principal investigator but will continue their scheduled 30 follow-up visits, if possible. Participants classified into category II (crossover to known 31 invasive therapy) will be taken off coded medication but will continue their scheduled 32 follow-up visits, if possible. Participants classified into category II prior to clinical 33 progression of BPH (category I) will remain classified as category II (i.e., never be classified into category I). Participants classified into category III (non-compliance with 34

the coded medication) will continue to be followed, if possible, and will eventually be classified into either categories I, II, or IV by the end of the trial.

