The primary analysis will be the time to clinical progression of BPH (i.e., time to category I). Participants in categories II through IV at the end of the trial will be censored as of the date of their last completed visit. A supportive analysis will be the time to the first occurrence of clinical progression of BPH (category I) or crossover to known invasive therapy (category II). For this analysis, participants in categories III or IV at the end of the trial will be censored as of the date of their last completed visit.

B. Secondary Research Questions

Although time to clinical progression of BPH is the primary outcome of the study, a key secondary objective of the study will include an assessment of:

- 1. The natural history of BPH in a well-defined cohort of men.
- Other secondary objectives of the study will include assessing differences over time between the four treatment groups with regard to:
 - 2. AUA symptom score and impact index
 - 3. Medical Outcomes Study (MOS) 36-Item Short Form Health Survey score
 - Maximal uroflow

C. Subgroup Hypotheses

Other hypotheses concern whether treatment response or progression of disease in the placebo and three treatment arms are the same or different in subgroups classified by:

- 1. AUA symptom score and impact index
- 2. MOS-36 Health Survey score
- Maximal uroflow
- 4. Residual urine
- Prostate volume

D. Substudy - Ultrasound, Biopsy of the Prostate and Hormones

A key feature of this protocol is the inclusion of predetermined tissue biopsies that will be obtained to evaluate the status of the prostate before and after medication in approximately half of the randomized participants. During the biopsy of the prostate, the participants will undergo transrectal ultrasound (TRUS) of the biopsy to assess differences over time between the four treatment groups with regard to prostate

volume. In addition, a serum sample will be forwarded to the diagnostic center for analysis of hormones (testosterone, dihydrotestosterone, and luteinizing hormone).

The purpose of this substudy is to provide additional information regarding the histopathobiology of BPH and to test the existing biomarkers for their prognostic ability regarding response to therapy. Specific studies to be carried out can be divided according to phases of BPH development as follows:

- 7 1. Proliferation: Immunohistochemical localization of MIB-1 nuclear proliferation antigen.

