Participants who elect to receive coded medications at the last follow-up visit scheduled within September 1, 2001 to November 30, 2001 will be assessed for adverse events at 3 months after the last scheduled follow-up visit, and for compliance to treatment regimen and adverse events at a final separation visit. Unused coded medications will be returned to the clinic and treatment group assignment will be disclosed to the participant at the separation visit.

Participants who elect not to receive coded medications at the last follow-up visit will be scheduled for a final separation visit to disclose treatment group assignment.

1. Discontinuation of the Follow-up Protocol

The occurrence or presence of the following will constitute discontinuation of the scheduled follow-up protocol:

- 1. Inactive follow-up. (a) Voluntary withdrawal by the participant, or (b) any condition which, in the opinion of the principal investigator, makes it unsafe for the participant to continue.
- 2. Death.

2. Abbreviated Follow-up Protocol for Prostate and Bladder Cancer

Randomized participants with a diagnosis of prostate cancer who elect "watchful waiting" will continue their coded medication and scheduled follow-up visits. For participants with prostate or bladder cancer that are receiving a known therapy for their prostate cancer or have any bladder-sparing procedure for their bladder cancer (e.g. TURBT), a simplified follow-up protocol will be initiated. This abbreviated follow-up protocol will be limited to the AUA symptom questionnaire (Appendix B) administered at quarterly follow-up visits and the MOS-36 Health Survey (Appendix D) administered at annual follow-up visits. For participants with bladder cancer that undergo a cystectomy for their bladder cancer, the abbreviated protocol will be limited to the MOS-36 Health Survey (see Appendix H) only, administered at annual follow-up visits. Participants with prostate or bladder cancer that enroll in a prostate or bladder cancer study,

respectively, will be handled on a case-by-case basis by the Clinical Review Subcommittee.

C. Participant Management Protocols

1. Blood Pressure Control

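### Men who cross over to invasive therapy stay in the primary risk set although no event can then be recorded for them, so the hazard ratio depends on how often each arm crosses over

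*Protocol*

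**What the plan says.** Section 3.A sorts participants into four categories. Category I is clinical progression, the primary event. Category II is crossover to known invasive therapy before progression. Three statements in that section bear on category II:

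- A man who enters it before progressing "will remain classified as category II (i.e., never be classified into category I").
- He stops coded medication but goes on attending scheduled visits, if possible.
- For the primary analysis, "Participants in categories II through IV at the end of the trial will be censored as of the date of their last completed visit".

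Section 8.C (Primary Endpoint) adds no crossover date. Men are administratively censored "if they complete the full duration of the trial without clinical progression of their BPH", and those who stop attending early are censored at their last follow-up visit. The planned methods are Kaplan-Meier estimates, the logrank test and the Cox model. Section 8.C also states: "Crossover to known invasive therapy prior to clinical progression of BPH may be considered a competing risk event". It responds with a composite of progression or crossover, whichever comes first, which Section 3.A calls supportive.

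**The concern.** Taken together, the rules give a crossed-over man follow-up time during which he is counted at risk but cannot have an event. How long this lasts depends on when he crosses over and how long he keeps attending.

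In a logrank or Cox analysis this time enlarges the denominator of the arm he belongs to. If crossover differs by arm, the denominators are inflated unequally, and the estimated effect on progression picks up part of the effect on the decision to treat invasively. The stated primary question concerns progression alone. The design has little power to spare, and Section 8.A makes no allowance for crossover.

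The composite is not affected, because crossover is an event there. It answers a different question, however, and does not correct the primary test.

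**Working it through.** **1. Inputs from the protocol (Section 8.A).** Placebo incidence 25% over 5 years; two-sided alpha 0.05 with Bonferroni over three comparisons, so 0.05/3 each; 80% power; one-third reduction, taken as a hazard ratio of 2/3; 2 years of accrual and 4 to 6 years of follow-up; 5% per year loss; 700 per arm.

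Placebo hazard: −ln(0.75)/5 = 0.0575 per year. Active hazard: 0.0575 × 2/3 = 0.0384.

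**2. Reproducing the plan's sample size.** Exponential formula with uniform accrual R = 2, total duration T = 6 and loss hazard η:

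- P(λ) = λ/(λ+η) × {1 − [exp(−(λ+η)(T−R)) − exp(−(λ+η)T)] / [(λ+η)R]}
- φ(λ) = λ²/P(λ)
- n per arm = [z(α)·√(2φ(mean λ)) + z(power)·√(φ(λ1)+φ(λ2))]² / (λ1−λ2)²

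This gives 616 per arm without losses (stated 612) and 693 with 5% loss (stated 688). Power at 700, 600 and 500 per arm is 80.5%, 73.1% and 63.9% (the protocol states 72% and 63% for the last two). The inputs are therefore read as the plan intended.

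**3. Hazard seen by the primary analysis.** Let λ be the progression hazard and k the crossover hazard, assumed exponential and independent of progression. At time t the fraction still able to have an event is exp(−(λ+k)t). The fraction crossed over but retained is k/(λ+k) × [1 − exp(−(λ+k)t)]. The apparent hazard is

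λ·exp(−(λ+k)t) / {exp(−(λ+k)t) + k/(λ+k)·[1 − exp(−(λ+k)t)]}.

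Example at 5 years, with assumed crossover of 2% per year on placebo and 1% on active:

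- Placebo: 0.0575 × 0.6786 / (0.6786 + 0.0829) = 0.0513
- Active: 0.0384 × 0.7852 / (0.7852 + 0.0444) = 0.0363
- Ratio: 0.708, against 0.667 at time zero

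**4. Whole-trial hazard ratio and power.** Expected logrank and Cox calculation with 700 per arm, 5% loss and true ratio 2/3. With p the active share of the risk set, U is the sum of active events minus p × all events, V is the sum of all events × p(1−p), and power = Φ(|U|/√V − 2.394). Without crossover this gives 80.7%. Crossover rates are assumptions, in % per year:

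| Placebo / active | HR, retained | Power, retained | Power, censored at crossover |
|---|---|---|---|
| 1 / 1 | 0.667 | 79.5% | 79.6% |
| 3 / 3 | 0.668 | 77.0% | 77.5% |
| 2 / 1.33 | 0.679 | 74.7% | 79.0% |
| 2 / 1 | 0.684 | 72.8% | 79.2% |
| 3 / 1 | 0.701 | 65.4% | 78.8% |
| 1 / 2 | 0.651 | 84.0% | 79.0% |

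With censoring at crossover the ratio is 0.667 in every row. Event counts are identical under the two rules (148 placebo and 106 active in the 2/1 row), so the whole difference comes from the risk-set denominators. The ratio is undisturbed when active crossover is about 1.03 times placebo crossover.

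**5. The placebo curve.** The 5-year cumulative incidence of progression with crossover as a competing event is λ/(λ+k) × [1 − exp(−5(λ+k))]. For k = 0.02 this is 0.0575/0.0775 × (1 − 0.6786) = 23.8%. At 1% and 3% per year it is 24.4% and 23.3%. The curve from the retained risk set takes these same values.

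**The case against.** The strongest reply is that keeping men at risk after a competing event is a recognised construction. The apparent hazard in step 3 is the subdistribution hazard, and the resulting curve is the correct share of men who progress before invasive therapy. A reader might infer that the placebo natural-history curve is biased low; step 5 shows that it is not. For the natural-history objective in Section 3.B that curve is a sensible quantity. What remains is that the protocol nowhere names a subdistribution analysis and poses its primary question about progression alone.

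A reader might also infer that the rule always dilutes the drug effect. It does not: equal crossover leaves the ratio essentially unchanged, and more crossover on active drug exaggerates the benefit. Larger placebo excesses than those in the table can be imagined, but nothing in the protocol supports any particular rate. The 2/1.33 row, where crossover falls by the same third as progression, costs about 4 points of power.

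Censoring at crossover is not free of assumptions either. Men sent to invasive therapy may be close to progression, so the censoring may be informative. The comparison above assumes independence and does not test it. This objection stands, and it is why the composite must be kept.

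Intent-to-treat does not rescue the rule. An intent-to-treat count would include progression after crossover, which Section 3.A bars. Category III men, by contrast, are followed and can still become events.

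Finally, one might extend the point to men on the abbreviated cancer follow-up in Section 6.B.2. The text does not support that: it reduces data collection (after cystectomy, to the MOS-36 only) but does not bar these men from category I.

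**Conclusion.** The point holds in a conditional form. As written, the primary logrank and Cox analyses retain men for whom an event has been ruled out, and the hazard ratio then depends on arm-specific crossover that the design does not model. The direction is not fixed by the text. A placebo excess is plausible if the drugs work, and the loss is then about 4 to 13 points of power over the assumed rates of 2/1.33 to 3/1% per year (79.0 − 74.7 = 4.3; 78.8 − 65.4 = 13.4).

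These sizes rest on assumed crossover rates, constant hazards, crossover independent of progression, and crossed-over men attending as long as other men. Neither unconditional dilution nor a biased placebo curve follows from the documents. The rule still needs correcting, because it governs the primary test and its result is not a clean effect on progression.

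**What to change.** In Section 3.A, replace the censoring sentence for the primary analysis with one saying that category II participants are censored at the date of crossover to invasive therapy, and categories III and IV at the last completed visit. Put the same rule in Section 8.C and state there that the primary logrank and Cox analyses estimate the cause-specific effect on progression.

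Add the cumulative incidence of progression with crossover as a competing event, for the natural-history objective. Keep the progression-or-crossover composite and describe it as the check on informative censoring.

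The cost is a few sentences. The crossover date is already needed for the composite, so no data or participants are added. The small downside is reliance on non-informative censoring at crossover, which the composite is there to examine.
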